5. Assess HIV testing and STI screening patterns at index oral or LA PrEP initiation and within 12-months following index PrEP initiation among people who initiate a PrEP regimen
6. Describe demographic and clinical characteristics, HIV testing and diagnoses, as well as STI screening and diagnoses over a 12-month period of follow-up among people who are not on PrEP but could benefit from PrEP

Study Design

Design: Cohort study using secondary data from electronic medical records in the OPERA cohort.

Exposure groups: Oral PrEP, LA PrEP

Duration of study:

- Analysis #1: 2021 to 2023 (Obj 1-1a); 21DEC2021 to 30JUN2024 (Obj 2-6)
- Analysis #2: 2021 to 2024 (Obj 1-1a); 21DEC2021 to 30JUN2025 (Obj 2-6)

Population

(Obj 1) People in OPERA aged ≥ 18 years with ≥ 1 clinical encounter during the calendar year of interest and no evidence of prior HIV diagnosis.

(Obj 1a) People with an incident HIV diagnosis identified in Obj 1.

(Obj 2-5) People without HIV in OPERA aged ≥ 18 years who initiated any new PrEP formulation during the study period with or without prior PrEP use.

(Obj 6) People without HIV in OPERA aged ≥ 18 years who could benefit from PrEP and are not on PrEP

Variables

Exposures:

- PrEP use (never, use within ≤ 12 months before diagnosis, use > 12 months before diagnosis)
- Time-updated PrEP type (oral or LA)

Outcomes:

- Incident HIV diagnosis: New HIV diagnosis *and/or* detectable HIV RNA *and/or* positive antigen/antibody test
- PrEP coverage: Proportion of days of access to oral PrEP or proportion of days of coverage by CAB LA
- HIV testing/STI screening: frequency and type of tests performed

Data Sources

OPERA cohort, a multi-site observational database built from the complete patient health records managed in electronic health record (EHR) systems throughout the US.

Study Size

Between 21DEC2021 and 30JUN2023 (Analysis # 1 inclusion period), 22,234 adults without HIV started a new PrEP formulation in OPERA. The first formulation used during the study period was TAF/FTC oral (n=12,110, 54%), TDF/FTC oral (n=9,740, 44%), or CAB LA (n=384, 2%). An additional 292 individuals switched to CAB LA PrEP later during the study period, for a total of 767 people receiving CAB LA injections during the Analysis #1 inclusion period.

Protocol for Non-Interventional Studies PASS Studies and Non-PASS Studies (4.0) March 2024

Template Doc ID: TMF-15706807

Parent Doc ID: VQD-SOP-066694

Data Analysis

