7. RESEARCH METHODS

7.1. Study Design

A cohort study using secondary data from the OPERA[®] (Observational Pharmacology Epidemiology Research & Analysis) cohort will be used to answer the study objectives. OPERA is a multi-site observational database collecting data prospectively from the complete electronic health records (EHR) from clinical care throughout the US.

[figure not shown]
Analyses to meet the study objectives will be conducted twice during the study period. Analysis #1 will include data from 01JAN2021-31DEC2023 (Obj. 1-1a) and from 21DEC2021 to 30JUN2024 (Obj 2-6). Analysis #2 will be a repeat of Analysis #1 with data from 1JAN2021-31DEC2024 (Obj. 1-1a) and from 21DEC2021 to 30JUN2025 (Obj 2-6). A

summary of the study design is provided in Table 1 (exposure groups, index date, censoring criteria, endpoints) and in Figure 1 (timeline).

Table 1. Summary of study design

		Analysis #1	Analysis #2
Obj 1 Among all people without HIV in OPERA	Exposure groups	Calendar years	Calendar years
	Index date	NA	NA
	Censoring criteria	NA	NA
	Endpoints	HIV diagnosis	HIV diagnosis
Obj 1a Among people with a new HIV diagnosis	Exposure groups	PrEP use (never, use within ≤12 months before diagnosis, use >12 months before diagnosis)	PrEP use (never, use within ≤12 months before diagnosis, use >12 months before diagnosis)
	Index date	Date of HIV diagnosis	Date of HIV diagnosis
	Censoring criteria	NA	NA
	Endpoints	NA	NA
Obj 2-5 Among PrEP users	Exposure groups	Oral PrEP, CAB LA PrEP	Oral PrEP, CAB LA PrEP
	Index date	Start of first PrEP regimen during the study period	Start of first PrEP regimen during the study period
	Censoring criteria	Death, loss to follow-up (12 months after last clinical contact), study end (30JUN2024), 12 months after index date	Death, loss to follow-up (12 months after last clinical contact), study end (30JUN2025), 12 months after index date
	Endpoints	HIV diagnosis, PrEP coverage, HIV testing, STI screening, STI diagnoses	HIV diagnosis, PrEP coverage, HIV testing, STI screening, STI diagnoses
Obj 6 Among people who could benefit from PrEP	Exposure groups	NA	NA
	Index date	First OPERA visit with indication for PrEP during study period	First OPERA visit with indication for PrEP during study period
	Censoring criteria	Death, loss to follow-up, study end (30JUN2024), 12 months after index date, PrEP initiation	Death, loss to follow-up, study end (30JUN2025), 12 months after index date, PrEP initiation

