7.2. Study Population and Setting

7.2.1. Inclusion Criteria

People without HIV in OPERA (Obj 1)

- i. ≥ 1 clinical encounter in OPERA during the calendar year of interest
- ii. ≥ 18 years old at the first clinical encounter during the calendar year of interest
- iii. No evidence of prior HIV diagnosis

People with a new HIV diagnosis (Obj 1.a)

- i. Incident HIV diagnosis (new HIV diagnosis/positive HIV test/detectable HIV RNA viral load) identified in Obj 1

PrEP users (Obj 2-5)

- i. HIV-negative
- ii. ≥ 18 years of age
- iii. Started any new PrEP formulation
 - Analysis #1: between 21DEC2021 and 30JUN2023
 - Analysis #2: between 21DEC2021 and 30JUN2024
- iv. With or without prior PrEP use (a different formulation or a gap ≥ 61 days without any PrEP immediately prior to the index PrEP; the same formulation may have been used ≥ 61 days before starting the index PrEP)

People who could benefit from PrEP (Obj 6)

- i. HIV-negative
- ii. ≥ 18 years of age

- iii. ≥ 1 clinical encounter in OPERA during the inclusion period
 - Analysis #1: between 21DEC2021 and 30JUN2023
 - Analysis #2: between 21DEC2021 and 30JUN2024
- iv. Any of the following indications for PrEP¹¹:
 - Bacterial STI in past 12 monthsⁱ (gonorrhea, syphilis, chlamydia)⁷
 - Alcohol use disorder⁷
 - Illicit non-injection drug use⁷
 - Injection drug use^{7, 14}
 - Black women¹⁴
 - Transgender women¹⁴
 - Men who have sex with men¹⁴
 - All individuals aged 18-24 yearsⁱⁱ¹⁴
 - Any history of PrEP use

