7.7.1. Primary analysis

7.7.1.1. Main Analytical approach

People without HIV in OPERA (Obj 1)

For each calendar year, the number and percentage of new HIV diagnoses will be reported out of all individuals receiving care at an OPERA clinic.

People with a new HIV diagnosis (Obj 1.a)

Among newly diagnosed people with HIV, PrEP use (never, use within ≤ 12 months before diagnosis, use > 12 months before diagnosis) and PrEP characteristics will be described using counts and proportions for categorical variables and median and interquartile ranges for continuous variables.

PrEP users (Obj 2-5)

(Obj 2) Baseline demographic and clinical characteristics will be described at the start of PrEP use during the study period, by regimen type (oral or LA), using median and interquartile ranges for continuous variables and counts and proportions for categorical variables.

Individuals contributing to both the oral and CAB LA PrEP groups may be included in both groups.

(Obj 3) The number, percentage, and incidence rate (per 100 person-years) of incident HIV diagnoses within 12 months of starting index PrEP and through study end will be described by route of administration (time-updated, oral or LA). The timing of HIV testing relative to PrEP start and HIV diagnosis will be described to assess to possibility of attributing HIV acquisition to the correct PrEP type. Incidence rates of HIV diagnoses (per 100 person-years) within 12 months of start and through study end will be estimated using time-updated univariate Poisson regression for each regimen type (time-updated, oral vs LA) to account for varying duration of follow-up.

(Obj 4) The percentage of days with access to oral PrEP and the percentage of days with coverage by CAB LA PrEP will be described over the first 12 months after index PrEP initiation.

(Obj 5) The frequency and rate (per 100 person-years) of HIV testing, STI screening, and STI diagnoses at index PrEP initiation and in the 12-months after index PrEP initiation.

Characteristics of the tests conducted will also be described. Frequency and type of tests

performed will be described by type of healthcare provider ordering the test and clinic type. Rates of HIV and STI tests over the first 12 months will be estimated using time-updated univariate Poisson regression for each regimen type (oral vs LA).

People who could benefit from PrEP (Obj 6)

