Baseline demographic and clinical characteristics will be described at the first OPERA visit with a PrEP indication, using median and interquartile ranges for continuous variables and counts and proportions for categorical variables. The frequency and rate (per 100 person-years) of HIV testing, HIV diagnoses, STI screening, and STI diagnoses will be described at the first OPERA visit with a PrEP indication and in the 12-months after the first indication.

Characteristics of the tests conducted will also be described. Frequency and type of tests performed will be described by type of healthcare provider ordering the test and clinic type. Rates of HIV tests and diagnoses as well as STI tests and diagnoses over the first 12 months will be estimated using time-updated univariate Poisson regression

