ANNEX 1 TABLES

Table shells for Analysis #1 are presented. Tables will be identical for Analysis #2, with the exception that study periods will be updated.

Table 1. Identification of the population of people without HIV in OPERA (Analysis #1)

	Included N (%)	Excluded N (%)
All individuals in OPERA		
≥1 clinical encounter between 01JAN2021 and 31DEC2021		
≥18 years old at first clinical encounter in 2021		
No evidence of HIV diagnosis before the first clinical encounter in 2021 [2021 pop]		
≥1 clinical encounter between 01JAN2022 and 31DEC2022		
≥18 years old at first clinical encounter in 2022		
No evidence of HIV diagnosis before the first clinical encounter in 2022 [2022 pop]		
≥1 clinical encounter between 01JAN2023 and 31DEC2023		
≥18 years old at first clinical encounter in 2023		
No evidence of HIV diagnosis before the first clinical encounter in 2023 [2023 pop]		

Table 2. Annual HIV incidence among people without HIV (Analysis #1)

	People without HIV, N	Incident HIV, ^a n (%)
2021		
2022		
2023		

^a New HIV diagnosis or positive HIV test (RNA, antigen/antibody)

Table 3. PrEP use among people with incident HIV (Analysis #1)

	People with incident HIV ^a N =
Never received PrEP, n (%)	
Ever received PrEP, n (%)	
Total number of days on PrEP, median (IQR) ^b	
Number of PrEP formulations received	
1, n (%)	
2, n (%)	
3, n (%)	
Any gaps between formulations, n (%) ^c	
Duration of gaps between formulations, median (IQR)	
PrEP use within ≤12 months before/on HIV diagnosis, n (%)	
Oral PrEP, n (%)	
TDF/FTC, n (%)	
TAF/FTC, n (%)	
CAB LA, n (%)	
Past PrEP use >12 months before HIV diagnosis, n (%)	
Oral PrEP, n (%)	
TDF/FTC, n (%)	
TAF/FTC, n (%)	
CAB LA, n (%)	

^a New HIV diagnosis or positive HIV test (RNA, antigen/antibody)

^b Including all formulations; gaps without PrEP do not count toward the total number of days on PrEP

^c Gap ≥31 days after oral PrEP, gap ≥37 days after first CAB LA injection, or gap ≥67 days after 2nd or subsequent CAB LA injection

Table 4. Identification of the PrEP users population

	Included N (%)	Excluded N (%)
All individuals in OPERA		
Ever received a PrEP prescription/injection in OPERA while HIV negative		
Start a new PrEP formulation (TDF/FTC, TAF/FTC, CAB LA) ^a between 21DEC2021 and 30JUN2023		
≥18 years old at start of index PrEP regimen		

^a Switch from one formulation to another or return to the same formulation after a pause ≥61 days without PrEP

Table 5. PrEP formulations used among PrEP users

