	Oral PrEP N=	CAB LA PrEP N=
HIV testing on schedule (oral: every 3 months (76-104 days); CAB LA: ±14 days of each injection), n (%)		
STI screening every 3 months (76-104 days) ^c , n (%)		
STI screening every 6 months (168-196 days) ^d , n (%)		
STI screening every 12 months (351-379 days) ^e , n (%)		
HIV testing NOT on schedule (oral: every 3 months (76-104 days); CAB LA: ±14 days of each injection), n (%)		
STI screening every 3 months (76-104 days) ^c , n (%)		
STI screening every 6 months (168-196 days) ^d , n (%)		
STI screening every 12 months (351-379 days) ^e , n (%)		

\$(vault:document_date__v)

Protocol for Non-Interventional Studies PASS Studies and Non-PASS Studies (4.0) March 2024

Template Doc ID: TMF-15706807

Parent Doc ID: VQD-SOP-066694

Table 26. STI diagnoses among PrEP users^a

	Oral PrEP N=	CAB LA PrEP N=
STI diagnosis within 14 days before/on day of PrEP type start, n (%)		
Any, n (%)		
Syphilis, n (%)		
Gonorrhea, n (%)		
Chlamydia, n (%)		
Chancroid, n (%)		
Lymphogranuloma venereum, n (%)		
Mycoplasma genitalium, n (%)		
Herpes Simplex-2, n (%)		
Trichomoniasis, n (%)		
Human papilloma virus/genital warts, n (%)		
HBV, n (%)		
HCV, n (%)		
STI diagnosis within 12 months after PrEP type start, n (%)		
Any, n (%)		
Syphilis, n (%)		
Gonorrhea, n (%)		
Chlamydia, n (%)		
Chancroid, n (%)		
Lymphogranuloma venereum, n (%)		
Mycoplasma genitalium, n (%)		
Herpes Simplex-2, n (%)		
Trichomoniasis, n (%)		
Human papilloma virus/genital warts, n (%)		
HBV, n (%)		
HCV, n (%)		

^a Tests are only counted for the PrEP type used at the time of diagnosis

Table 27. Incidence rate of STI diagnoses within 12 months of index among PrEP users^a

	Oral PrEP N=	CAB LA PrEP N=
Total # STI diagnoses within 12 months of index, n		
Person-years of follow-up		
IR per 100 py (95% CI)		

Table 28. Identification of the people who could benefit from PrEP population

	Included N (%)	Excluded N (%)
All individuals in OPERA		
≥1 clinical encounter between 21DEC2021 and 30JUN2023		
≥18 years old at first clinical encounter in study period		
Any indication for PrEP ^a		
No PrEP use between 21DEC2021 and 30JUN2023		

^a Bacterial STI in past 12 months (gonorrhea, syphilis, chlamydia), alcohol use disorder, illicit non-injection drug use, injection drug use. Black woman, transgender woman, men who have sex with men, aged 18-24 years, any history of PrEP use

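### Objective 6 describes HIV diagnoses at the index visit itself, which contradicts its HIV-negative entry criterion and leaves open whether HIV already present counts in the incidence rate

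*Protocol*

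**What the plan says.** All references are to the Protocol.

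- **Outcome window, section 7.7.1.1 (Obj 6).** The frequency and rate per 100 person-years are to cover "HIV diagnoses, STI screening, and STI diagnoses will be described at the first OPERA visit with a PrEP indication and in the 12-months after". Its model sentence reads "Rates of HIV tests and diagnoses as well as STI tests and diagnoses over the first 12 months will be estimated using time-updated univariate Poisson". It does not say whether the day of the index visit counts.
- **Index date, section 7.1, Table 1.** For Obj 6 it is "First OPERA visit with indication for PrEP during study period", the same visit at which outcomes are to be described.
- **Entry, section 7.2.1.** The first Obj 6 criterion is "i. HIV-negative", worded exactly as for PrEP users. The synopsis agrees: "People without HIV in OPERA aged ≥ 18 years who could benefit from PrEP and are not on PrEP". Neither says when or how that status is established.
- **Rate definition elsewhere.** The synopsis analysis text places the Obj 6 rate over 12 months of follow-up. Section 7.3.2 places it after index, although it anchors the window to a PrEP start that this group does not have, and it censors follow-up at HIV diagnosis.
- **Cohort construction, Annex 1.** Table 28 has steps for an encounter, for age ("≥18 years old at first clinical encounter in study period"), for an indication and for no PrEP use. It has no HIV step. Table 4 for PrEP users includes "Ever received a PrEP prescription/injection in OPERA while HIV negative".
- **PrEP users, section 7.7.1.1.** Obj 3 counts "incident HIV diagnoses within 12 months of starting index PrEP and through study end". The at-index outcomes in Obj 5 are HIV testing, STI screening and STI diagnoses; HIV diagnosis is not among them.

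**The concern.** A person whose HIV is found in a sample from the index visit was almost certainly infected before follow-up began. That is a prevalent case. It belongs in a percentage of people found positive at the visit, not in a rate of new infections. Because follow-up is censored at HIV diagnosis, such a case would add one event and essentially no time at risk. A rate per 100 person-years at a visit also has no meaning, since a visit has no duration.

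What is at stake is the HIV rate in Annex Table 35, the study's only incidence rate for people with a PrEP indication who are not on PrEP. Incidence in this setting is low, so a small share of people positive at index could make up much of the numerator.

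**Working it through.** The protocol gives no expected HIV rate, event count or sample size for Obj 6, so there is no planned figure to reproduce. The check is a comparison of the text, followed by an illustration on assumed inputs.

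**1. Two readings of the entry criterion**

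- *Status judged at the index visit.* Anyone found positive that day is not HIV-negative and never enters. The index-visit HIV diagnoses promised in section 7.7.1.1 are then zero by construction, and the Table 35 rate is unaffected.
- *Status judged on earlier records only.* A person first found positive at the index visit enters and is reported as an outcome.

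The second reading is realistic for two reasons. Table 28 has no step that would remove such a person. The protocol also uses this convention already: the Obj 1 shell (Annex Table 1) excludes only HIV evident before the first encounter of the calendar year. A programmer carrying that rule over to Obj 6 would admit index-visit positives. A negative test near baseline appears in Table 35 only as a reported count and percentage, and it is tied to the start of a PrEP type.

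**2. Size under the second reading**

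Let p be the share first found positive at index, m the mean follow-up in years of the others, and r the true rate per 100 person-years. If N people enter, person-years are N(1 − p)m, and the index-visit cases add

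100 × p / [(1 − p) m] per 100 person-years.

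The multiplier is 1 plus that amount divided by r. None of p, m or r is in the document. The assumed ranges are p from 0.05% to 0.5%, m from 0.6 to 1.0 and r from 0.3 to 1.0.

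- Smallest effect (p = 0.05%, m = 1.0, r = 1.0): 100 × 0.0005 / 0.9995 = 0.05, so the multiplier is 1 + 0.05/1.0 = 1.05.
- Largest effect (p = 0.5%, m = 0.6, r = 0.3): 100 × 0.005 / (0.995 × 0.6) = 0.84, so the multiplier is 1 + 0.838/0.3 = 3.79.
- Middle case (m = 0.8, r = 0.5):

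| p | added per 100 PY | reported rate | multiplier |
|---|---|---|---|
| 0.05% | 0.06 | 0.56 | 1.13 |
| 0.1% | 0.13 | 0.63 | 1.25 |
| 0.2% | 0.25 | 0.75 | 1.50 |
| 0.5% | 0.63 | 1.13 | 2.26 |

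Under the first reading, or if the index day is left out of the Poisson numerator, the multiplier is 1.0. The honest range is therefore from no effect to several-fold.

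**The case against.** The strongest reply is that the protocol already excludes these people. Obj 6 carries the same HIV-negative criterion as the PrEP users, and the synopsis repeats it. The passages that define the rate (synopsis, section 7.3.2, the Poisson sentence, the title of Table 35) refer to 12 months of follow-up or to the time after index, and no table shell has a row for HIV diagnosed at the index visit. The section 7.7.1.1 sentence may simply set four outcomes against two time points without care. Handling of day 0 is also commonly left to the statistical analysis plan, which is not at hand.

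Much of this stands. It means that entry of index-visit cases into the Table 35 rate is one reading and not a certainty. It does not remove the conflict: the protocol states an outcome window that its own entry criterion makes empty or wrong, and its cohort table lacks the step that would decide which. That is a contradiction in the text, not a detail left for later.

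A reader might go further and infer that only the non-PrEP group is exposed to this bias, so that the study would flatter PrEP. The documents do not support that. The HIV-negative criterion is the same in both groups. PrEP users need no documented negative test either: Table 9 only reports how many had one within two weeks before or on the start, so undetected HIV at start can enter Table 10 as well. The study is described as descriptive, with no confounders considered, and it plans no comparison of Table 35 with Table 10. Readers may set the two tables side by side, but that would be their comparison. The difference the text does show is narrower: only Obj 6 names HIV diagnosis as an at-index outcome, and only its selection table omits the HIV step.

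**Conclusion.** The point holds as an internal contradiction with a possible bias. Section 7.7.1.1 conflicts with section 7.2.1 on whether HIV can be found at index, and with the synopsis and section 7.3.2 on the window for the rate. Table 28 leaves the question open. Followed as written, section 7.7.1.1 and Table 28 together allow prevalent HIV with almost no person-time into an incidence rate.

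The size cannot be derived from the document. Under the assumed inputs the rate would be multiplied by 1.05 to 3.79 if index-visit cases are counted, and by 1.0 if they are not. These multipliers illustrate why the wording matters; they are not estimates for this cohort. The point should be settled before the Obj 6 tables are programmed.

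**What to change.** - In section 7.7.1.1, remove HIV diagnoses from the outcomes described at the first visit with an indication. HIV testing, STI screening and STI diagnoses at that visit are outside this point.
- In section 7.2.1 and Annex Table 28, add a step that excludes anyone with an HIV diagnosis or a positive sample dated on or before the index visit. Dating by the sample matters, because a result from the index-visit sample may be recorded some days later.
- Start HIV events and person-time the day after the index visit, and state this in section 7.3.2, where the window now refers to a PrEP start.
- Report HIV found at the index visit as a separate percentage, outside Table 35, with everyone meeting the other entry criteria as the denominator.
- If a sensitivity analysis is restricted to people with a negative test after index, start the clock at that test. Otherwise the time from index to the test is event-free by selection and biases the rate downward.

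The cost is a few sentences, one selection step and one table row, with no new data. A few events leave the rate. The change does not remove undetected HIV in people who were not tested at index; that remains a limitation in both groups.

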7.7.1.2. Data handling conventions

The data used for this research study are not identifiable by the research staff. However, all data, even when stripped of identifiers, are handled and treated, in motion and at rest, as though the data could be identified. All data are managed according to U.S. regulations such as HIPAA and HITECH. These regulations and guidelines expand upon the ethical principles detailed in the 1964 Declaration of Helsinki.

7.8. Quality control and Quality Assurance

This study will be conducted according to local quality control processes. This procedure requires documented evidence that the study protocol has been correctly interpreted and executed.

Epididian has working practices & procedures governing the use of observational data, the development of analysis specifications and plans, the development of analytical programming and the analytical quality assurance (QA) process and the scientific review of reports as well as clinical advisory charters for the clinical review of output intended for public domain.

Working practices for the development of analysis specifications include basic identifying information, background material, relevant definitions of key study variables, population definitions, baseline definitions, specific requirements for dataset creation, and statistical requirements such as eligibility criteria, exposures, outcomes and model fitting. Working practices for programming include naming conventions, proper code documentation and commentary, content, appearance, efficiencies (i.e. use of macros), and organization of output, maintainability and generalizability. Working practices for programming QA include self-reviews of observational counts, missing data values, many-to-many merges, variable formatting, numeric-character & character-numeric conversions, uninitialized variables, unresolved macro references, report completeness and report-to-specification correspondence, and system errors and logs. The QA team review may include small sample spot-checking, coding log reviews, complete coding review, selected observations from intermediary dataset reviews, and/or independent programming to reproduce the results. Documentation of non-public domain reports includes market, scientific, statistical, and clinical review. Documentation of scientific protocols, reports and manuscripts intended for

public domain follows two sequential steps: an internal-to-Epividian epidemiological, statistical, and clinical review, followed by a clinical/epidemiological external advisory board review.

All analytical data, coding algorithms, QA documentation and report outputs will be retained per Epividian standard practices. Figure 2 presents an overview of study processes.

CCI

